10.2 Statistical Methods

10.2.1 Intention-to-Treat

The intention-to-treat (ITT) population will include all subjects who were randomized to study treatment in the randomized part of the study. In analyses based on the ITT population, subjects will be assigned to the treatment group they were randomized to. Subjects in the non-randomized group will be analyzed in the "Normal Level" group.

10.2.2 General Considerations

All efficacy analyses will be performed using the ITT population. For this Pilot study, no adjustments for multiplicity will be carried out. All statistical tests will be performed using two-sided tests with a 0.025 level of significance unless otherwise specified.

Continuous variables will be summarized using descriptive statistics, i.e. number of subjects (N), mean, median, standard deviation, 25th percentile, 75th percentile, minimum and maximum. Categorical variables will be summarized using frequencies and percentages.

10.2.3 Analysis for the Primary Endpoint

The primary endpoint of 3-year PFS will be presented using Kaplan-Meier curves and will be presented for the normal serum Vitamin D control group and the low and high dose randomized groups. Each randomized group (low and high dose) will be compared to a historical fixed expected 3-year PFS of 45% using a one-sample logrank test following the method of Woolson (1981)⁴⁵.

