10.1 Patient Accrual

Subjects found to have low levels of serum Vitamin D <30 ng/ml at time of enrollment will be randomized on a 1:1 basis to receive vitamin D 5000 IU daily (Higher Dose Cohort) or vitamin D 1000 IU daily (Lower Dose Cohort) stratified by disease group aggressive NHL (fast-growing tumors) or indolent NHL/CLL (slow-growing tumors).

The sample size calculations are based on the primary endpoint of 3-year PFS. The expected PFS for patients with low levels of serum Vitamin D is 45%.⁴⁴ The 3 year PFS of the low dose and high dose groups will each be compared to a historical fixed expected 3-year PFS of 45%.⁴⁴ The sample size calculations are based on a single arm survival calculation based on an assumption of exponentially distributed PFS times using a 3-year PFS of 60% for each of the randomized arms (low dose or high dose). Therefore, the sample size calculations are based on detecting a 15% difference in 3-year PFS for each randomized arm (low dose or high dose) vs.

a historical fixed expected PFS of 45%. Since such single arm studies are typically conducted as a one-sided test, we use $\alpha = 0.025$, however, no other adjustments will be made for multiplicity. Sample size calculations were conducted using the SWOG statistical calculator found at https://www.swogstat.org/stat/public/one_survival.htm.

Using a one sided test with accrual time of 2 years, follow-up time of 3 years, $\alpha = 0.025$, a null PFS of 45% and an alternative PFS of 60% a total of 230 eligible patients will be enrolled in the normal serum Vitamin D group based on current accrual rate and until 70 eligible patients in each randomized arm (low or high dose) to provide 80% power. These results assume that two sequential tests are made (1 interim analysis and the final analysis) using the O'Brien-Fleming spending function to determine the test boundaries. Our final enrollment is projected to be 370 patients expecting a ~10% loss to follow-up/inevaluability rate.

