10.4 Stopping Rules

10.4.1 Interim Analyses

One interim monitoring analysis for efficacy will be conducted after n=35 patients in each randomized arm (35 patients in the low dose group and 35 patients in the high dose group) have enrolled. Two separate tests will be conducted to compare 1- the PFS in the low dose arm to the fixed expected value of 45% and 2- the PFS in the high dose arm to the fixed expected value of 45%. We will use an O'Brien-Fleming-type spending function to assess whether the interim results are sufficient to conclude that vitamin D supplementation in either the low dose or high dose arm is effective in increasing the PFS to 60%. The monitoring boundary p-values associated with the 1 interim look using the O'Brien-Fleming spending function will be 0.001525 with the final analysis being done with p=0.024501. The type I error associated with this monitoring plan is approximately 0.025. If $\geq 10\%$ of patients in either Vitamin D arm has severe adverse events that are felt to be directly related to the Vitamin D supplement, the study will be stopped.

Section 11.0 Records to Be Kept:

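### With 70 patients per arm, the Woolson test named for the primary analysis has about 78% power on the plan's own inputs, not the stated 80%

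*Combined protocol and SAP*

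**What the plan says.** Section 10.1 sizes each randomized arm by a single-arm calculation "based on an assumption of exponentially distributed PFS times", with 3-year PFS of 45% under the null and 60% under the alternative. The design inputs are given as "Using a one sided test with accrual time of 2 years, follow-up time of 3 years", with alpha 0.025, and accrual runs "until 70 eligible patients in each randomized arm (low or high dose) to provide 80% power". The section names a web calculator but no test statistic.

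Section 10.2.3 compares each arm with the fixed 45% "using a one-sample logrank test following the method of Woolson (1981"). It does not write out the statistic, gives no size or power for it at 70 patients, and specifies no small-sample correction.

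Section 10.4.1 adds one efficacy look after 35 patients per arm have enrolled. The nominal levels "will be 0.001525 with the final analysis being done with p=0.024501". It names no separate statistic for that look.

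**The concern.** The power statement and the primary test sit in different sections, and nothing shows that the 80% was calculated for the finite-sample behaviour of the named test. Woolson's statistic divides by the square root of E, the expected number of events. With few events it has a short lower tail (fewer events than expected, benefit) and a long upper tail (harm). The plan tests only for benefit, so the distortion falls on the side where it costs power. A reader who relies on 80% would be relying on a figure that the named test does not reach, and part of the allotted alpha would go unspent.

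**Working it through.** **Inputs.** From 10.1: S0(3) = 0.45, S1(3) = 0.60, exponential PFS, one-sided 0.025, 2 years of accrual, 3 years of follow-up, n = 70. From 10.4.1: final level 0.024501, interim level 0.001525. Assumptions of this check: uniform entry, no loss, the exponential null of 10.1 carried into the test (the documents fix only the 3-year value), and Woolson's statistic taken as (O−E)/√E.

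**Step 1, hazards.** λ = −ln S(3)/3. λ0 = 0.7985/3 = 0.2662 and λ1 = 0.5108/3 = 0.1703 per year; the ratio is 0.640.

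**Step 2, expected events.** P(event) = 1 − [exp(−3λ) − exp(−5λ)]/(2λ).
- Null: 1 − (0.4500 − 0.2643)/0.5323 = 0.651, or 45.6 events in 70 patients.
- Alternative: 1 − (0.6000 − 0.4268)/0.3406 = 0.491, or 34.4 events.

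**Step 3, reproducing the 80%.** Two routes reach it.
- Exponential rate on the cube-root scale, with s = λ^(1/3)/(3√D) and D the expected events. The difference is 0.6433 − 0.5543 = 0.0890, s0 = 0.03176 and s1 = 0.03150. Then z = (0.0890 − 1.960 × 0.03176)/0.03150 = 0.849, so power is 80.2% and 70 is the smallest sufficient n.
- Large-sample Woolson formula. Under the alternative E averages 34.40/0.640 = 53.78. Then z = (53.78 − 34.40 − 1.960 × √53.78)/√34.40 = 5.00/5.87 = 0.853, so power is 80.3%.

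Log-hazard versions give 82.1% or 74.5% depending on the variance used, and an untransformed hazard gives 73.9%. The stated figure therefore reproduces, but it does not identify the statistic behind it.

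**Step 4, actual size and power at n = 70.** Simulated with 1.5 million trials per hypothesis, O = events and E = λ0 × total follow-up time. The simulation error on power is about √(0.776 × 0.224/1,500,000) = 0.03 points.

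| Final test | Level | Size | Power |
|---|---|---|---|
| Woolson (O−E)/√E | 0.025 | 1.96% | 77.9% |
| Woolson (O−E)/√E | 0.024501 | 1.92% | 77.6% |
| Signed-root likelihood ratio | 0.025 | 2.50% | 80.7% |
| Signed-root likelihood ratio | 0.024501 | 2.45% | 80.5% |

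The signed-root form is Z = sign(O−E) × √{2[O ln(O/E) − (O−E)]}, from the same O and E. Woolson's skewness shows in its two tails under the null at nominal 0.025: 1.96% for benefit and 3.2% for harm.

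**Step 5, sample size for Woolson's form.** At the final level, simulated power is 79.9% with 74 patients per arm and 80.4% with 75.

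**Step 6, the interim look.** The two nominal levels spend 0.0250 in total at half information, so the boundary itself is in order. When 35 patients per arm have enrolled, about 4.1 events are expected under the null and 2.7 under the alternative.

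| Interim / final statistic | Interim size | Overall size | Power |
|---|---|---|---|
| Woolson / Woolson | 0.00% | 1.92% | 77.6% |
| Signed-root / signed-root | 0.39% | 2.80% | 80.7% |
| Woolson / signed-root | 0.00% | about 2.4% | about 80.5% |

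**Step 7, if follow-up is cut at 3 years for everyone.** At 0.025, Woolson has size 1.85% and power 69.0%; signed-root has size 2.46% and power 72.9%.

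**The case against.** The strongest reply is that nothing was mis-sized. A reader might infer from the exponential assumption in 10.1 that the 80% belongs to a different, exponential-model test. The documents do not support that: 10.1 gives a distributional assumption and a calculator, not a statistic, and the large-sample Woolson formula also gives 80.3%. This part of the reply stands. What is left is a gap between an asymptotic formula and the test's real behaviour at this size, and that gap exists whichever formula was used.

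The reply also holds that the effect is small and safe. That stands too. The gap is about 2 to 2.5 points, false positives are rarer than planned, and this is a pilot with two arms each tested at 0.025 and no multiplicity adjustment. Woolson's is a published and cited test, and keeping it is defensible if the power figure is corrected.

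Finally, replacing the statistic is not a free change if it is applied throughout. With about 4 events at the interim, the signed-root form would spend 0.39% where 0.1525% is planned, and overall size would be about 2.8%. This objection is met only by confining the signed-root form to the final analysis.

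**Conclusion.** The point holds in a limited form. On the plan's own inputs the named test has size of about 1.9% and power of about 77.5 to 78%, against the stated 2.5% and 80%. The figures rest on exponential PFS, uniform entry, 3 to 5 years of follow-up, no loss, and Woolson's statistic in the (O−E)/√E form.

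Two stronger conclusions should not be drawn. Type I error is not inflated; it is below nominal. And the signed-root form does not secure 80% in general: it does so only with the full 3 to 5 years of follow-up and no loss. Other features of the plan move power more. Besides the 3-year cut in step 7, a 10% loss leaving 63 patients per arm gives Woolson power of about 73%; the projected total of 370 equals 230 + 2 × 70, so the 70 carries no allowance for that loss.

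**What to change.** Minimum change: in 10.1, state that the power of Woolson's test with 70 patients per arm is about 78% on the plan's inputs. This is one line and needs no patients or data.

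Alternative, to be adopted only before outcome data are examined:
- In 10.2.3, specify that the final analysis uses Z = sign(O−E) × √{2[O ln(O/E) − (O−E)]}, one-sided at 0.024501, with Woolson's form as a sensitivity analysis. Write the formula out: the signed square root of Woolson's own chi-square is the same test and changes nothing, and 2(√O − √E) exceeds nominal size (2.7%).
- In 10.4.1, state that the interim look keeps Woolson's form. The signed-root form should not be used there as the look is now timed.

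The alternative costs two sentences and gives up about 0.5 points of unplanned conservatism (1.92% to about 2.4%) for about 3 points of power (77.6% to about 80.5%).

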10.2.4 Analysis for the Secondary Endpoint

The secondary endpoint of 3-year OS will be analyzed as described for the primary endpoint, using a historical fixed outcome of 80%.⁴⁵

10.2.5 Safety

The incidence of adverse events (AEs) and serious adverse events (SAEs) will be described for the low dose and high dose groups and compared between groups using a Chi-square. The frequency of occurrence of overall toxicity, categorized by toxicity grades, will be described for the low dose and high dose groups and compared between groups using a Chi-square.

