5.1 Randomization plan

This is a randomized study. All subjects will have a serum 25-hydroxyvitamin D [25(OH) D] drawn at time of enrollment. (NOTE: Only subjects currently taking < 1000 IU Vitamin D supplements are eligible for screening.) Subjects found to have **low levels** of serum 25-hydroxyvitamin D [25(OH) D] <30 ng/ml will be randomized on a 1:1 basis to vitamin D 5000 IU daily (Higher Dose Cohort) or vitamin D 1000 IU daily (Lower Dose Cohort) and stratified by disease group (aggressive NHL or indolent NHL/CLL).

The randomization schedule is generated by the study statistician. The randomization schedule is then provided to the UNMC research pharmacist.

Site study personnel will complete the Subject Randomization Request for those subjects meeting criteria for randomization and submit this along with the registration request documents outlined in Section 4.2 to the UNMC project coordinator. The UNMC research pharmacist will assign a randomization number and cohort. When finalizing the registration procedures, the randomization assignment is sent to study personnel by the UNMC project coordinator.

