5.2 Evaluations

Pre-treatment Evaluations Within One Month (30 Days) of Consent:

- History and physical
- Calcium level
- Serum 25-hydroxyvitamin D [25(OH) D]
- Height and weight
- Vital signs, including blood pressure

If subjects have a **normal level** of serum 25-hydroxyvitamin D [25(OH) D] ≥ 30 ng/ml at time of enrollment, the subject will automatically be enrolled in the controlled group and will be followed only for long-term progression free survival and outcome. No further evaluation of serum 25-hydroxyvitamin D [25(OH) D] will be obtained. (NOTE: Subjects currently taking Vitamin D supplements will be encouraged to continue their supplementation.)

If subjects are found to have **low levels** of serum 25-hydroxyvitamin D [25(OH) D] <30 ng/ml at time of enrollment, the subjects will be randomized to receive either vitamin D 5000 IU (5 tablets) daily (Higher Dose Cohort) or vitamin D 1000 IU (one tablet) daily (Lower Dose Cohort) for three years. To provide a means of ensuring oral routes of medication adherence of patients while participating in a clinical trial, **Appendix D** “Oral, Sublingual, and/or Buccal Route Medication Adherence Standard Procedure (V 1.0 11-25-2013)” will be followed. (NOTE: Subjects who were currently taking Vitamin D supplements at the time of screening will be asked to discontinue the use of their Vitamin D supplementation and use only the Vitamin D dosing and supply instructed by the study.)

UNMC subjects will take oral over the counter supply through UNMC pharmacy.

Subjects at affiliate and Non-UNMC IRB approved sites will take oral over the counter Vitamin D 1000 IU (vitamin D-3, (cholecalciferol)) tablets. Investigators will need to prescribe the appropriate dose in which the subject is randomized.

Follow-up Evaluations

Subjects randomized to the Vitamin D cohorts: at 6 months, 12 months, and year 2 and 3 (Day 1095) (+/- 30 days) from registration confirmation:

- Serum 25-hydroxyvitamin D [25(OH) D] (Levels will be measured at a location convenient for the patient, for example, at their local primary care provider office.)

After year 3 (1095 days), the investigator will discuss continuation of Vitamin D supplementation recommendations with the subject. The supply of any recommendations for continued Vitamin D will be at the subjects cost.

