6.1 Toxicity criteria

This trial will assess only the grade 3 and 4 toxicities related to the Vitamin D administration. The NCI Common Toxicity Criteria Adverse Events (CTCAE) Version 4 (Appendix B) will be used to grade toxicity. It is available at the following internet site:

http://ctep.cancer.gov/protocolDevelopment/electronic_applications/ctc.htm#ctc_40

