8.1.7 Toxicology

Toxicity due to vitamin D is considered to manifest at serum levels greater than 150 ng/mL of 25-hydroxyvitamin D. Symptoms of hypervitaminosis D include fatigue, nausea, vomiting, and weakness associated with hypercalcemia. (Page 27 sites more toxicity details)

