This product may adversely interact with certain health and medical conditions, other prescription and over-the-counter drugs, foods, or other dietary supplements. This product may be unsafe when used before surgery or other medical procedures. It is important to fully inform your doctor about the herbal, vitamins, mineral or any other supplements you are taking before any kind of surgery or medical procedure. With the exception of certain products that are generally recognized as safe in normal quantities, including use of folic acid and prenatal vitamins during pregnancy, this product has not been sufficiently studied to determine whether it is safe to use during pregnancy or nursing or by persons younger than 2 years of age.

Section 9.0 Toxicity Reporting Guidelines:

This protocol will comply with monitoring and adverse event reporting requirements of the UNMC/Fred & Pamela Buffett Cancer Center Data Monitoring plan. The protocol will adhere to the institutional and FDA guidelines for the toxicity reporting.

Grade 3 and 4 adverse events (AEs) related to the Vitamin D administration will be graded according to the National Cancer Institute Common Terminology, Criteria for Adverse Events (NCI-CTCAE), version 4.0, which can be accessed at the following URL.

http://ctep.cancer.gov/protocolDevelopment/electronic_applications/ctc.htm#ctc_40

The over the counter agent used in the protocol is commercially available with a well-characterized toxicity profile.

All subjects will be closely followed for grade 3 and 4 toxicity/adverse events related to the Vitamin D administration from the time that the first dose of study drug is administered and ending 30 days following the final therapy. Adverse events will be assessed by reports from subjects of Vitamin D related grade 3 or higher adverse events to their physician-investigators, standard laboratory results and by physical examinations. Vitamin D related Only **prescription** medication taken to relieve symptoms of the Vitamin D related AE will be recorded in addition to the outcome. All other/routine concomitant medications WILL NOT be recorded. Deaths occurring within 30 days of study treatment regardless of relationship will be reported to the UNMC DSMC. Only fatal AEs will be reported to the UNMC IRB per the IRB's policy and procedures.

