9.2.1 IRB Reporting

All Vitamin D related internal serious adverse events (SAEs) must be reported to the local IRB promptly per institutional human research protection program policies.

9.2.2 Fred & Pamela Buffett Cancer Center Data and Safety Monitoring Committee (DSMC) Reporting

All Vitamin D related adverse events grade 3 or higher (expected or unexpected) will be reported to the University of Nebraska Medical Center, Fred & Pamela Buffett Cancer Center Data and Safety Monitoring Committee (DSMC) in accordance with DSMC guidelines.

In its initial review, the DSMC will make a recommendation for the frequency of DSMC monitoring based on an assessment of risk associated with study-associated therapy, per the DSMC policy.

Detailed policy and procedures for this section may be reviewed at:

<http://www.unmc.edu/cancercenter/clinical/prms.html>

Attribution of AE: The likelihood of relationship of the AE to the study drugs will be determined by the investigator based on the following definitions:

- **Not Related:** The subject was not exposed to the study treatment or another cause is obvious.
- **Probably Not Related:** The AE is most likely explained by another cause, and the time of occurrence of the AE is not reasonably related to the study treatment.
- **Possibly Related:** Study treatment administration and AE occurrence reasonably related in time, and the AE is explained equally well by causes other than study treatment, or treatment administration and AE occurrence are not reasonably related in time, but the AE is not obviously a result of other causes.
- **Probably Related:** Study treatment administration and AE occurrence are reasonably related in time, and the AE is more likely explained by study treatment than by other mechanisms.
- **Definitely Related:** There occurrence and timing of the AE are clearly attributable to the study treatment.

Severity Grade of AE. The severity of events reported on the AE case report form will be determined by the principal investigator according the NCI Common Toxicity Criteria (CTC version 4.0). Copies of the AE report will be submitted to the IRB as indicated in Section 9.1.1.

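### The plan's only between-dose test, the 10.2.5 safety Chi-square, counts events that investigators who know the dose have attributed to vitamin D, so it may measure attribution rather than dose

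*Combined protocol and SAP*

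**What the plan says.** **The test.** Section 10.2.5 states that the incidence of AEs and SAEs "will be described for the low dose and high dose groups and compared between groups using a Chi-square", and it treats toxicity by grade the same way. PFS and OS (10.2.3, 10.2.4) and the interim look (10.4.1) each compare one arm with a fixed value. No test is named for serum vitamin D. Section 10.2.2 sets a two-sided 0.025 level by default.

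**What is counted.** Section 6.1: "This trial will assess only the grade 3 and 4 toxicities related to the Vitamin D administration". Section 9.0 follows the same events, starting from "reports from subjects of Vitamin D related grade 3 or higher adverse events to their physician-investigators" together with standard laboratory results and examinations. Relatedness is part of the AE and SAE definitions (9.1.1, 9.1.2). Section 9.2.2 widens the grade to 3 or higher for reporting. Deaths within 30 days go to the DSMC whatever their cause, but 10.2.5 does not bring them into the test.

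**Who decides, and what they know.** Relatedness "will be determined by the investigator based on the following definitions" (9.2.2). In 5.1, "the randomization assignment is sent to study personnel by the UNMC project coordinator". In 5.2, for affiliate and other non-UNMC sites, "Investigators will need to prescribe the appropriate dose in which the subject is randomized", and patients take five tablets or one. No section masks the dose or provides for attribution without knowledge of it.

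**The safety stop.** Section 10.4.1 applies if at least 10% of patients in either vitamin D arm have "severe adverse events that are felt to be directly related to the Vitamin D supplement, the study will be stopped".

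**The concern.** A comparison of randomised arms is protected against bias only if the events are counted in the same way in both. Here each event must pass a causal judgement made with the dose known before it enters the count. 1000 IU is the smallest intake that excludes a candidate already taking a supplement (3.2), so an event on five tablets may be easier to blame than one on a single tablet.

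The material leaves room for judgement. Section 8.1.7 says "Symptoms of hypervitaminosis D include fatigue, nausea, vomiting, and weakness associated with hypercalcemia", while Section 2.0 lists fatigue among lymphoma symptoms. Timing, on which the 9.2.2 scale leans, separates little when dosing is daily for three years. Serum calcium is scheduled only before treatment (Section 7.0). Events judged unrelated are not in the planned data, so the filter cannot be removed at analysis.

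At stake is the trial's one statement about relative safety at 5000 and 1000 IU. A significant result could come from unequal blame. A null result could mean only that nothing was blamed on either dose.

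**Working it through.** **Plan figures.** The plan gives no figure for the safety comparison. Its 70 per arm (10.1) comes from PFS and can be reproduced. With exponential PFS, 45% v 60% at 3 years, 2 years of accrual and 3 of follow-up, the hazard ratio is 0.640, the event probability under 60% is 0.4915, and the expected count under the null hazard is 0.4915/0.6397 = 0.7683. Then n = (1.960√0.7683 + 0.842√0.4915)² / (0.7683 − 0.4915)² = 69.5, rounded up to 70. So n = 70 per arm is sound as an input, but it was not chosen for safety.

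**Step 1: how few calls matter.** With n = 70 per arm and counts 0 v k, the uncorrected Pearson statistic is 140(70k)² / [70·70·k·(140−k)]. The critical value at two-sided 0.025 is 5.024.

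- k = 4: 4.118, p = 0.042.
- k = 5: 5.185, p = 0.023.

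Five attributed patients against none reach significance with the uncorrected test. The expected count in each event cell is then only 5/2 = 2.5. For 5 v 0, the continuity-corrected statistic is 140(350−70)² / (4900·5·135) = 3.319, p = 0.069, and Fisher's test gives p = 0.058. The plan does not say whether a correction is used.

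**Step 2: illustration under assumed rates.** None of these rates is in the documents. Let q be the proportion with an eligible grade 3+ event, equal in both arms (no dose effect). Let a_L and a_H be the proportions attributed on 1000 and 5000 IU. The recorded counts are Binomial(70, q·a_L) and Binomial(70, q·a_H). The rejection rate sums their joint probability over all tables that the test rejects.

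| a_L v a_H | q = 10% | 20% | 30% | 40% |
|---|---|---|---|---|
| 5% v 5% | 0.00% | 0.07% | 0.29% | 0.65% |
| 5% v 10% | 0.05% | 0.67% | 2.15% | 3.94% |
| 5% v 20% | 0.93% | 7.59% | 16.62% | 24.56% |
| 5% v 30% | 4.20% | 22.50% | 39.65% | 54.76% |
| No filter | 2.41% | 2.50% | 2.57% | 2.49% |

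Equal attribution of 10% or 20% in both arms gives at most 2.2%. The excess therefore comes from unequal attribution, not from the Chi-square itself.

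**Step 3: sensitivity.** With the continuity-corrected test, the q = 40% column becomes 0.6% (5% v 10%), 12.2% (5% v 20%) and 40.6% (5% v 30%); Fisher's test gives the same values. The level of attribution matters as well as the ratio. Uncorrected, 10% v 20% gives 3.9% to 9.0% for q of 20% to 40%, and 25% v 50% gives 11.7% to 28.0%. At q = 5%, even 5% v 30% gives only 0.3%.

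**Step 4: the safety stop.** Seven of 70 is 10%. In the 5000 IU arm, P(X ≥ 7) for q of 10% to 40% is 0.05% to 32.7% at 20% attribution and 0.5% to 75.0% at 30%. These figures apply only if the stop uses the same calls, which the plan does not state.

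**The case against.** **The harm is assumed.** No event rate, attribution rate or attribution gap is documented. Sections 8.1.6 and 8.4 expect adverse events to be rare, and rare events leave the test little chance to reject at all. This stands, and it is why no size can be claimed. It does not rescue the comparison, because near-zero counts in both arms would then say little about relative safety.

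**Attribution is constrained.** The symptoms in 8.1.7 are tied to hypercalcemia. 25(OH)D is measured at 6, 12, 24 and 36 months, and routine laboratory results feed the assessment. Section 9.1.1 admits events that are only possibly related, so ambiguous events should qualify in both arms. This stands in part: these anchors narrow the judgement, but the dose is still known when it is made. A lenient threshold also raises the attribution level, and at a higher level a twofold gap has more effect (Step 3).

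**Five calls settling the test is partly a small-cell effect.** This stands. It depends on the uncorrected statistic and is a separate matter from attribution.

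**The stop.** A reader might infer that the 10% rule uses the same investigator judgement as 10.2.5. The documents do not support that. Section 10.4.1 names no judge, and its wording is stricter than the AE definition. Related grade 3+ events also go to the DSMC, and the study is audited at least semi-annually. What can be said is that the rule rests on a relatedness judgement whose maker and cut-off are not given.

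**Low consequence.** Safety is not a stated objective, and this is a pilot. This stands for severity. Recording only related events is also a reasonable choice for a low-risk supplement. The problem is testing those counts between doses.

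**Conclusion.** The point holds as a limit on interpretation. The only between-dose test uses counts filtered by a judgement made with the dose known, so its result may reflect attribution rather than harm. Knowledge of dose is inferred from the procedures in 5.1 and 5.2; the protocol does not call itself open-label.

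The size cannot be derived from the documents. With 5% attribution on 1000 IU, a twofold gap has little effect (at most 3.9% against 2.5%). A four- to sixfold gap could matter, less so with a corrected or exact test. A reader might infer that the comparison is bound to be biased against 5000 IU, or that the efficacy findings are compromised. The text supports neither: no attribution gap is documented, and the PFS and OS tests do not use these counts. Severity is minor to moderate.

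**What to change.** **If collection is still open**, add to 6.1 and 9.0: *At the 6, 12, 24 and 36 month AE checks in both randomised arms, every grade 3 or higher hypercalcemia, nausea, vomiting, fatigue, weakness or kidney stone is recorded, whether or not it is attributed to vitamin D.* In 10.2.5: *The between-arm comparison uses these events regardless of attribution. Investigator-attributed events are reported beside it, descriptively.*

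**If collection is closed**, list attributed events by arm without a p-value, labelled as investigator-attributed with dose known. Add n (%) by arm with a scheduled 25(OH)D above 100 ng/ml and the resulting hold, as a measure of exposure and not of toxicity. That threshold largely tracks dose: at about 1 ng/ml per 100 IU (2.5), a baseline below 30 rises to below about 40 on 1000 IU and 80 on 5000 IU. It also lies below the 150 ng/ml toxicity level in 8.1.7.

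**Cost.** At most 140 × 4 = 560 existing checks with six tick-box terms each (3,360 items), plus chart review for past visits. No dose-masked physician is needed. The downside is a little more recording, and dilution of a small true effect by events due to lymphoma or chemotherapy. Whether holds are coded in the database is not stated; Section 11.1 keeps the reasons for dose changes in the research chart.
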